#### **8.4. Medication Errors**

Medication errors may result, in this study, from the administration or consumption of the wrong product, by the wrong subject, at the wrong time, or at the wrong dosage strength. Such medication errors occurring to a study participant are to be captured on the medication error CRF which is a specific version of the AE page, and on the SAE form when appropriate. In the event of medication dosing error, the sponsor should be notified immediately.

Medication errors are reportable irrespective of the presence of an associated AE/SAE, including:

- Medication errors involving subject exposure to the investigational product;
- Potential medication errors or uses outside of what is foreseen in the protocol that do or do not involve the participating subject;
- Administration of a dose other than that specified in the protocol, Note: Missed doses of investigational product are not considered to be a medication error;
- Administration of investigational product in which deviations from the protocol-specified storage and refrigeration requirements have been noted (except those approved by the Pfizer study team);
- Administration of ETN from a commercial supply rather than ETN labeled for investigational use (unless specifically instructed to do so by the Pfizer study team);
- Administration of the investigational product to anyone other than the subject.

Whether or not the medication error is accompanied by an AE, as determined by the investigator, the medication error is captured on the medication error version of the AE page and, if applicable, any associated AE(s) are captured on an AE CRF page.

#### **8.5. Abnormal Test Findings**

The criteria for determining whether an abnormal objective test finding should be reported as an AE are as follows:

- Test result is associated with accompanying symptoms; and/or
- Test result requires additional diagnostic testing or medical/surgical intervention; and/or
- Test result leads to a change in study dosing or discontinuation from the study, significant additional concomitant drug treatment, or other therapy; and/or
- Test result is considered to be an AE by the investigator or sponsor.

Merely repeating an abnormal test, in the absence of any of the above conditions, does not constitute an AE. Any abnormal test result that is determined to be an error does not require reporting as an AE.

## **8.6. Serious Adverse Events**

A serious adverse event is any untoward medical occurrence at any dose that:

- Results in death;
- Is life-threatening (immediate risk of death);
- Requires inpatient hospitalization or prolongation of existing hospitalization;
- Results in persistent or significant disability/incapacity (substantial disruption of the ability to conduct normal life functions);
- Results in congenital anomaly/birth defect;
- Lack of efficacy should be reported as an AE when it is associated with an SAE.

Medical and scientific judgment is exercised in determining whether an event is an important medical event. An important medical event may not be immediately life-threatening and/or result in death or hospitalization. However, if it is determined that the event may jeopardize the subject or may require intervention to prevent one of the other AE outcomes, the important medical event should be reported as serious.

Examples of such events are intensive treatment in an emergency room or at home for allergic bronchospasm; blood dyscrasias or convulsions that do not result in hospitalization; or development of drug dependency or drug abuse.

### **8.6.1. Protocol-Specified Serious Adverse Events**

There are no protocol-specified SAEs in this study. All SAEs will be reported by the investigator as described in previous sections, and will be handled as SAEs in the safety database (see the section on [Serious Adverse Event Reporting Requirements](#)).

### **8.6.2. Potential Cases of Drug-Induced Liver Injury**

Abnormal values in AST and/or ALT levels concurrent with abnormal elevations in total bilirubin level that meet the criteria outlined below in the absence of other causes of liver injury are considered potential cases of drug-induced liver injury (potential Hy's law cases) and should always be considered important medical events.

The threshold of laboratory abnormalities for a potential case of drug-induced liver injury depends on the subject's individual baseline values and underlying conditions. Subjects who present with the following laboratory abnormalities should be evaluated further to definitively determine the etiology of the abnormal laboratory values:

- Subjects with AST or ALT and total bilirubin baseline values within the normal range who subsequently present with AST or ALT values  $\geq 3$  times the upper limit of normal ( $\times$  ULN) concurrent with a total bilirubin value  $\geq 2 \times$  ULN with no evidence of hemolysis and an alkaline phosphatase value  $\leq 2 \times$  ULN or not available;
- For subjects with preexisting ALT **OR** AST **OR** total bilirubin values above the ULN, the following threshold values should be used in the definition mentioned above:
  - For subjects with preexisting AST or ALT baseline values above the normal range: AST or ALT values  $\geq 2$  times the baseline values and  $\geq 3 \times$  ULN, or  $\geq 8 \times$  ULN (whichever is smaller).

Concurrent with

- For subjects with preexisting values of total bilirubin above the normal range: Total bilirubin level increased from baseline by an amount of at least  $1 \times$  ULN **or** if the value reaches  $\geq 3 \times$  ULN (whichever is smaller).

The subject should return to the investigational site and be evaluated as soon as possible, preferably within 48 hours from awareness of the abnormal results. This evaluation should include laboratory tests, detailed history, and physical assessment.

In addition to repeating measurements of AST and ALT, laboratory tests should include albumin, creatine kinase, total bilirubin, direct and indirect bilirubin, gamma-glutamyl transferase, prothrombin time (PT)/ international normalized ratio (INR), and alkaline phosphatase. A detailed history, including relevant information, such as review of ethanol, acetaminophen, recreational drug and supplement consumption, family history, occupational exposure, sexual history, travel history, history of contact with a jaundiced person, surgery, blood transfusion, history of liver or allergic disease, and work exposure, should be collected. Further testing for acute hepatitis A, B, or C infection and liver imaging (eg, biliary tract) may be warranted. All cases confirmed on repeat testing as meeting the laboratory criteria defined above, with no other cause for liver function test (LFT) abnormalities identified at the time, should be considered potential Hy's law cases irrespective of availability of all the results of the investigations performed to determine etiology of the abnormal LFTs. Such potential Hy's law cases should be reported as SAEs.

### **8.7. Hospitalization**

Hospitalization is defined as any initial admission (even less than 24 hours) in a hospital or equivalent healthcare facility or any prolongation of an existing admission. Admission also includes transfer within the hospital to an acute/intensive care unit (eg, from the psychiatric wing to a medical floor, medical floor to a coronary care unit, or neurological floor to a tuberculosis unit). An emergency room visit does not necessarily constitute a hospitalization; however, the event leading to the emergency room visit should be assessed for medical importance.

Hospitalization does not include the following:

- Rehabilitation facilities;
- Hospice facilities;
- Respite care (eg, caregiver relief);
- Skilled nursing facilities;
- Nursing homes;
- Same-day surgeries (as outpatient/same-day/ambulatory procedures).

Hospitalization or prolongation of hospitalization in the absence of a precipitating, clinical AE is not in itself an SAE. Examples include:

- Admission for treatment of a preexisting condition not associated with the development of a new AE or with a worsening of the preexisting condition (eg, for workup of persistent pre-treatment laboratory abnormality);
- Social admission (eg, subject has no place to sleep);
- Administrative admission (eg, for yearly physical examination);
- Protocol-specified admission during a study (eg, for a procedure required by the study protocol);
- Optional admission not associated with a precipitating clinical AE (eg, for elective cosmetic surgery);
- Hospitalization for observation without a medical AE;
- Preplanned treatments or surgical procedures. These should be noted in the baseline documentation for the entire protocol and/or for the individual subject;

Diagnostic and therapeutic noninvasive and invasive procedures, such as surgery, should not be reported as AEs. However, the medical condition for which the procedure was performed should be reported if it meets the definition of an AE. For example, an acute appendicitis that begins during the AE reporting period should be reported as the AE, and the resulting appendectomy should be recorded as treatment of the AE.

## 8.8. Severity Assessment

If required on the AE CRFs, the investigator will use the adjectives MILD, MODERATE, or SEVERE to describe the maximum intensity of the AE. For purposes of consistency, these intensity grades are defined as follows:

MILD	Does not interfere with subject's usual function.
MODERATE	Interferes to some extent with subject's usual function.
SEVERE	Interferes significantly with subject's usual function.

Note the distinction between the severity and the seriousness of an AE. A severe event is not necessarily an SAE. For example, a headache may be severe (interferes significantly with the subject's usual function) but would not be classified as serious unless it met one of the criteria for SAEs, listed above.

## 8.9. Causality Assessment

The investigator's assessment of causality must be provided for all AEs (serious and nonserious); the investigator must record the causal relationship in the CRF, as appropriate, and report such an assessment in accordance with the SAE reporting requirements if applicable. An investigator's causality assessment is the determination of whether there exists a reasonable possibility that the investigational product caused or contributed to an AE; generally the facts (evidence) or arguments to suggest a causal relationship should be provided. If the investigator does not know whether or not the investigational product caused the event, then the event will be handled as "related to investigational product" for reporting purposes, as defined by the sponsor (see the section on [Reporting Requirements](#)). If the investigator's causality assessment is "unknown but not related to investigational product," this should be clearly documented on study records.

In addition, if the investigator determines that an SAE is associated with study procedures, the investigator must record this causal relationship in the source documents and CRF, as appropriate, and report such an assessment in accordance with the SAE reporting requirements, if applicable.

## 8.10. Exposure During Pregnancy

For both unapproved/unlicensed products and for marketed products, an exposure during pregnancy occurs if:

1. A female becomes, or is found to be, pregnant either while receiving or having been exposed (eg, because of treatment or environmental exposure) to the investigational product; or the female becomes, or is found to be pregnant after discontinuing and/or being exposed to the investigational product;

An example of environmental exposure would be a case involving direct contact with a Pfizer product in a pregnant woman (eg, a nurse reports that she is pregnant and has been exposed to chemotherapeutic products).

2. A male has been exposed (eg, because of treatment or environmental exposure) to the investigational product prior to or around the time of conception and/or is exposed during his partner's pregnancy.

If a study subject or study subject's partner becomes or is found to be pregnant during the study subject's treatment with the investigational product, the investigator must submit this information to the Pfizer drug safety unit on an SAE Report Form and Exposure During Pregnancy (EDP) supplemental form, regardless of whether an SAE has occurred. In addition, the investigator must submit information regarding environmental exposure to a Pfizer product in a pregnant woman (eg, a subject reports that she is pregnant and has been exposed to a cytotoxic product by inhalation or spillage) using the EDP supplemental form. This must be done irrespective of whether an AE has occurred and within 24 hours of awareness of the exposure. The information submitted should include the anticipated date of delivery (see below for information related to termination of pregnancy).

Follow-up is conducted to obtain general information on the pregnancy and its outcome for all EDP reports with an unknown outcome. The investigator will follow the pregnancy until completion (or until pregnancy termination) and notify Pfizer of the outcome as a follow-up to the initial EDP supplemental form. In the case of a live birth, the structural integrity of the neonate can be assessed at the time of birth. In the event of a termination, the reason(s) for termination should be specified and, if clinically possible, the structural integrity of the terminated fetus should be assessed by gross visual inspection (unless preprocedure test findings are conclusive for a congenital anomaly and the findings are reported).

If the outcome of the pregnancy meets the criteria for an SAE (ie, ectopic pregnancy, spontaneous abortion, intrauterine fetal demise, neonatal death, or congenital anomaly [in a live-born baby, a terminated fetus, an intrauterine fetal demise, or a neonatal death]), the investigator should follow the procedures for reporting SAEs.

Additional information about pregnancy outcomes that are reported as SAEs follows:

- Spontaneous abortion includes miscarriage and missed abortion;
- Neonatal deaths that occur within 1 month of birth should be reported, without regard to causality, as SAEs. In addition, infant deaths after 1 month should be reported as SAEs when the investigator assesses the infant death as related or possibly related to exposure to the investigational product.

Additional information regarding the EDP may be requested by the investigator. Further follow-up of birth outcomes will be handled on a case-by-case basis (eg, follow-up on preterm infants to identify developmental delays). In the case of paternal exposure, the investigator will provide the study subject with the Pregnant Partner Release of Information Form to deliver to his partner. The investigator must document in the source documents that the subject was given the Pregnant Partner Release of Information Form to provide to his partner.

### **8.11. Occupational Exposure**

An occupational exposure occurs when, during the performance of job duties, a person (whether a healthcare professional or otherwise) gets in unplanned direct contact with the product, which may or may not lead to the occurrence of an AE.

An occupational exposure is reported to the drug safety unit within 24 hours of the investigator's awareness, using the SAE report form, regardless of whether there is an associated AE/SAE. Since the information does not pertain to a subject enrolled in the study, the information is not reported on a CRF; however a copy of the completed SAE report form is maintained in the investigator site file.

### **8.12. Withdrawal Due to Adverse Events (See Also the Section on [Subject Withdrawal](#))**

Withdrawal due to AEs should be distinguished from withdrawal due to other causes, according to the definition of AE noted earlier, and recorded on the appropriate AE CRF page.

When a subject withdraws because of an SAE, the SAE must be reported in accordance with the reporting requirements defined below.

### **8.13. Eliciting Adverse Event Information**

The investigator is to report all directly observed AEs and all AEs spontaneously reported by the study subject. In addition, each study subject will be questioned about AEs.

### **8.14. Reporting Requirements**

Each AE is to be assessed to determine if it meets the criteria for SAEs. If an SAE occurs, expedited reporting will follow local and international regulations, as appropriate.

#### **8.14.1. Serious Adverse Event Reporting Requirements**

If an SAE occurs, Pfizer is to be notified within 24 hours of investigator awareness of the event.

In particular, if the SAE is fatal or life-threatening, notification to Pfizer must be made immediately, irrespective of the extent of available AE information. This time frame also applies to additional new information (follow-up) on previously forwarded SAE reports as well as to the initial and follow-up reporting of EDP, exposure via breastfeeding, and occupational exposure cases.

In the rare event that the investigator does not become aware of the occurrence of an SAE immediately (eg, if an outpatient study subject initially seeks treatment elsewhere), the investigator is to report the event within 24 hours after learning of it and document the time of his or her first awareness of the AE.

For all SAEs, the investigator is obligated to pursue and provide information to Pfizer in accordance with the time frames for reporting specified above. In addition, an investigator may be requested by Pfizer to obtain specific additional follow-up information in an

expedited fashion. This information collected for SAEs is more detailed than that captured on the AE CRF. In general, this will include a description of the AE in sufficient detail to allow for a complete medical assessment of the case and independent determination of possible causality. Information on other possible causes of the event, such as concomitant medications, vaccines, and/or illnesses, must be provided. In the case of a subject death, a summary of available autopsy findings must be submitted as soon as possible to Pfizer or its designated representative.

#### **8.14.2. Nonserious Adverse Event Reporting Requirements**

All AEs will be reported on the AE page(s) of the CRF. It should be noted that the form for collection of SAE information is not the same as the AE CRF. Where the same data are collected, the forms must be completed in a consistent manner. For example, the same AE term should be used on both forms. AEs should be reported using concise medical terminology on the CRFs as well as on the form for collection of SAE information.

#### **8.14.3. Sponsor's Reporting Requirements to Regulatory Authorities**

AE reporting, including suspected unexpected serious adverse reactions, will be carried out in accordance with applicable local regulations.

### **9. DATA ANALYSIS/STATISTICAL METHODS**

Detailed methodology for summary and statistical analyses of the data collected in this study will be documented in a Statistical Analysis Plan (SAP), which will be maintained by the sponsor. This document may modify the plans outlined in the protocol; however, any major modifications of the primary endpoint definition and/or its analysis will also be reflected in a protocol amendment.

#### **9.1. Sample Size Determination**

The focus of this open label study is estimation. The sample size for this study was determined based on both the primary and key secondary endpoints. For the primary endpoint, 70% of subjects are expected to flare following treatment withdrawal. With an enrollment of approximately 200 subjects, approximately 96 subjects are expected to enter the treatment withdrawal period. If 70% of subjects with treatment withdrawn flare, the half width of the 95% confidence interval on flare rate estimate will be approximately 10%. For the key secondary endpoint of retreatment response, it is anticipated that 60% of the subjects who flare and are retreated will recover the initial ASDAS less than 1.3 response. The half-width confidence interval on this estimate will be approximately 12%.

#### **9.2. Efficacy Analysis**

##### **9.2.1. Analysis of the Primary Endpoint**

The primary endpoint, the occurrence of flare (ASDAS ESR greater than or equal to 2.1) in Period 2 will be summarized descriptively as the percent with flare with 95% confidence interval. This estimate will include all subjects who qualify for the retreatment interval and have at least one evaluation after treatment is withdrawn.

ASDAS is calculated from the following parameters:

1. Total back pain (BASDAI question 2);
2. Subject global assessment of disease activity;
3. Peripheral pain/swelling (BASDAI question 3);
4. Duration of morning stiffness (BASDAI question 6);
5. C-reactive protein (CRP) in mg/litre or ESR in mm/h.

The ASDAS score is then calculated as follows:

ASDAS CRP = (0.121 x total back pain) + (0.110 x subject global) + (0.073 x peripheral pain/swelling) + (0.058 x duration of morning stiffness) + (0.579 x Ln(CRP+1)).

ASDAS ESR = (0.08 x total back pain) + (0.11 x subject global) + (0.09 x peripheral pain/swelling) + (0.07 x duration of morning stiffness) + (0.29 x  $\sqrt{\text{ESR}}$ ).

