## **2. STUDY OBJECTIVES AND ENDPOINTS**

### **2.1. Objectives**

#### **2.1.1. Primary Objective**

- To estimate the proportion of subjects who flare within 40 weeks following withdrawal of ETN in subjects who have achieved ASDAS CRP less than 1.3 (inactive disease).

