#### **4.3. Inclusion Criteria – Period 3**

Subjects must meet the criteria for flare in order to be eligible to enter Period 3. Flare is defined as ASDAS ESR greater than or equal to 2.1.

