## **12. ETHICS**

### **12.1. Institutional Review Board/Ethics Committee**

It is the responsibility of the investigator to have prospective approval of the study protocol, protocol amendments, informed consent documents, and other relevant documents, eg, recruitment advertisements, if applicable, from the IRB/EC. All correspondence with the IRB/EC should be retained in the investigator file. Copies of IRB/EC approvals should be forwarded to Pfizer.

The only circumstance in which an amendment may be initiated prior to IRB/EC approval is where the change is necessary to eliminate apparent immediate hazards to the subjects. In that event, the investigator must notify the IRB/EC and Pfizer in writing immediately after the implementation.

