1. VERSION HISTORY

This Statistical Analysis Plan (SAP) for study B1801381 is based on the protocol dated 24JUN2015.

Table 1. Summary of Major Changes in SAP Amendments

| SAP Version | Location and Change | Rationale |
|-------------|--|--|
| 1 | Not Applicable | |
| 2 | Throughout Typo corrections | Clarification |
| | Section 3.1 Rearrange ASDAS section for clarity | Clarification |
| | Section 5.2.4 Modify time of relapse to be next scheduled visit for relapses at unscheduled visits – comparator study B1801031 did not have any option to identify flares at unscheduled visits | Clarification based on BDR 1 review |
| | Section 5.3 Added detail to define use of unscheduled visits in LOCF summaries | Clarification based on BDR 1 review |
| | Section 6.2.1 Corrected method of imputation, removed reference to logistic regression (all time to flare modelling will use Cox regression) and added specificity to results reporting. | Time to event specified LOCF, but no imputation is used. Changed univariate summaries of subgroup analysis of time to flare to use Cox models to use one consistent approach for modeling flare. |
| | Section 6.4 Changed method from logistic regression to Cox regression, added specificity to results reporting | Cox models to use one consistent approach for modeling flare. |
| | Appendix 1.1 Added NSAID classification for NSIADs not on original list | Added NSAIDS not in original classification list based on BDR 1 findings |

| | | |
|--|---|--|
| | 
Appendix 2 Clarified specification of endpoints to be presented by period 1 sustained ASDAS category (Y/N)
 | 
Clarification needed after review of BDR 1 tables.
 |
| | 
Appendix 3 Added. Visit windows defined to include unscheduled visits in tabulations
 | 
Requested by programming to document interactive decisions.
 |

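### Does the protocol restrict the primary flare estimate to subjects who have already flared?

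*Protocol*

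**What the plan says.** Protocol 9.2.1 summarises the primary endpoint, flare (ASDAS ESR of 2.1 or more) in Period 2, as a percentage with a 95% confidence interval. It then names the analysis set: "This estimate will include all subjects who qualify for the retreatment interval and have at least one evaluation after treatment is withdrawn". The Statistical Method part of the Protocol Summary repeats the sentence.

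Retreatment is Period 3 throughout the protocol. Section 4.3 states its entry condition: "Subjects must meet the criteria for flare in order to be eligible to enter Period 3".

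Other sections describe a different set for the primary estimate:

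- Protocol 2.1.1 (primary objective) concerns subjects who reached ASDAS CRP below 1.3 and then had etanercept withdrawn.
- Protocol 9.1 sizes the flare estimate on the withdrawal period: "approximately 96 subjects are expected to enter the treatment withdrawal period". It treats retreated subjects as the denominator of a separate estimate: "it is anticipated that 60% of the subjects who flare and are retreated will recover the initial ASDAS less than 1.3 response".
- SAP 6.1.1.1 runs the primary analysis on the Period 2 full analysis set (FAS). SAP 4.1.2 defines that set as subjects with at least one Period 2 evaluation and adds no flare requirement.

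**The concern.** A proportion whose denominator is selected on the outcome carries no information. If the set is restricted to subjects who qualify for retreatment, every member has flared by definition and the percentage with flare is fixed at 100%. The sentence appears in both places where the protocol defines the primary set, so it cannot be dismissed as a stray phrase in a summary.

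There is a procedural side as well. The SAP says it "is based on the protocol dated 24JUN2015", yet it uses a different set and its change table does not mention the difference. Protocol section 9 says that "any major modifications of the primary endpoint definition and/or its analysis will also be reflected in a protocol amendment", and Protocol 12.1 requires "prospective approval of the study protocol, protocol amendments" from the ethics committee. If the two documents really disagreed on who counts in the primary endpoint, that would be a substantive conflict that nobody had acknowledged.

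**Working it through.** **Inputs.** From Protocol 9.1: expected flare 70%; about 96 subjects entering withdrawal; stated half-width about 10%; expected recovery on retreatment 60%; stated half-width about 12%. From SAP 5.1: two-sided 95% intervals. I assume that every subject who flares is retreated.

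**1. The plan's own primary precision figure.** Wald half-width = 1.96 × √(p(1 − p)/n).

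- p = 0.70, n = 96: 1.96 × √(0.70 × 0.30/96) = 0.0917, or 9.2 points.
- Exact (Clopper-Pearson): 0.70 × 96 = 67.2, taken as 67 flares. 67/96 = 69.8%, interval 59.6% to 78.7%, half-width 9.6 points.

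Both agree with about 10%.

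**2. The plan's retreatment figure.** p = 0.60, n = 67: 1.96 × √(0.60 × 0.40/67) = 0.1173, or 11.7 points. Exact, 40/67: interval 47.0% to 71.5%, half-width 12.3 points. Both agree with about 12%. The roughly 67 subjects who flare are therefore the denominator for recovery, not for flare.

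**3. The literal set of 9.2.1.** 67/67 = 100%, exact interval 94.6% to 100%, Wald half-width 0. The half-width alone would not separate the two readings sharply, since 70% with n = 67 would give 11.0 points. What decides it is that a 70% flare rate is impossible in a set made up only of subjects who flared.

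**4. The sentence read on its own terms.** Its second condition asks for at least one evaluation after withdrawal. A flare can be established only by such an evaluation, so the condition would be redundant if the first one meant flarers. It does real work only if the first condition means subjects entering withdrawal.

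**5. What will be run.** SAP 6.1.1.1 with SAP 4.1.2 gives Period 2 subjects with at least one evaluation and no selection on flare. This matches the objective, section 9.1 and the sensible reading of 9.2.1.

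**The case for a change.** The strongest case for acting is that the sentence defines the primary analysis set, is wrong in both places, and is contradicted by a SAP that does not say so. The first two points are true. The third does not make it a breach of the amendment rule. Protocol section 9 lets the SAP modify the protocol's plans and reserves an amendment for major modifications of the primary endpoint or its analysis. If the protocol wording is a slip for the withdrawal period, the SAP carries out the intended analysis and modifies nothing. One cannot hold both that the wording is obviously a slip and that departing from it is a major modification.

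A second argument is that the SAP set does not match the protocol exactly either. SAP 4.1.2 asks for an evaluation during Period 2, and both documents say that the Week 24 visit marks the beginning of Period 2. A subject lost straight after Week 24 might then be counted or not. With 67 flares among 96 entrants, excluding 1 such subject moves the estimate from 69.8% to 67/95 = 70.5%, and excluding 5 moves it to 67/91 = 73.6%. Those are shifts of 0.7 and 3.8 points, but the counts of 1 and 5 are assumed; the documents give none.

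The SAP answers this elsewhere:

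- Appendix 2.3 closes the Week 24 window at Day 182 and opens Week 28 at Day 183, under a withdrawal interval labelled Weeks 28 to 64.
- Section 3.4 makes the last value before withdrawal the Period 2 baseline.
- Section 5.3 does not carry baseline forward unless otherwise noted, so under LOCF a subject seen only at Week 24 contributes no Period 2 value.
- Counting Week 24 would also empty the condition in 4.1.2, because every entrant needs a Week 24 ASDAS to qualify.

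What stands is that 4.1.2 could have said this in one clause.

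**Conclusion.** The concern is right about the words and wrong about the consequence. The set named in Protocol 9.2.1 and the Summary cannot be used literally, but it is a clerical slip: retreatment stands where withdrawal was meant. The objective, the sample size arithmetic, the sentence's own second condition and the SAP all point to the same intended set. No analyst could plausibly run the literal version, and the SAP gives the correct population explicitly.

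The effect on the planned estimate is nil: about 96 subjects, an expected 70%, and a half-width of 9 to 10 points all stand. A protocol amendment with ethics review for this sentence alone would change no conduct, sample size or analysis. The Week 24 question is settled by the SAP's windows and baseline rules, and the shifts shown for it rest on assumed counts.

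This conclusion assumes that the Period 2 FAS is built with the Appendix 2.3 windows, and that SAP 6.1.1.1 governs the primary analysis as written.
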